9.2.1.3 Dexamethasone

Dexamethasone will be taken by mouth or by IV infusion once-daily on Days 1 (\pm 2), 8 (\pm 2), and 15 (\pm 2) for all cycles and on Day 22 (\pm 2) of Cycles 1 through 8. Dexamethasone will be administered at least 30 minutes (but no more than 4 hours) prior to carfilzomib. Subjects receiving dexamethasone IV on Days 1, 8, and 15 may receive dexamethasone orally on Day 22.

9.2.2 *CARFILZOMIB AND LENALIDOMIDE DOSE MODIFICATION GUIDELINES*

Dose reduction levels of carfilzomib and lenalidomide for toxicity management of individual subjects are provided in [Table 5](#) and [Table 6](#), respectively:

Table 5 Dose Decrement for Carfilzomib

Nominal Dose (mg/m ²)	Reduced Carfilzomib Doses (mg/m ²)		
	Dose -1	Dose -2	Dose -3
20	Discontinue		
56	45	36	Discontinue
70	56	45	36

Table 6 Dose Decrement for Lenalidomide

Nominal Dose (mg)	Reduced Lenalidomide Doses (mg)		
	Dose -1	Dose -2	Dose -3
25	15	10	5
10	5	Discontinue	—

Treatment guidelines for specific hematologic toxicities are outlined in [Section 9.2.2.1](#) and nonhematologic toxicities in [Section 9.2.2.2](#). In addition to dose reductions, administration of carfilzomib and/or lenalidomide may be held temporarily in the event of a treatment-related toxicity at the investigator's discretion. When administration of carfilzomib and/or lenalidomide is held, the reason must be documented in the case report form (CRF), and the medical monitor must be notified within 2 business days of the scheduled dose ([Section 9.1](#)).

If either the lenalidomide or carfilzomib dose level is reduced during a given cycle, the reduced dose level will be continued for the next cycle. If the reduced dose level is tolerated for a complete cycle, the subject may, at the investigator's discretion, resume the dose level prior to the reduction at the start of the subsequent cycle.

Carfilzomib or lenalidomide can be discontinued in the event of a treatment-related toxicity that, in the opinion of the investigator, warrants discontinuation. The subject will be considered still on protocol treatment as long as carfilzomib is being administered.

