9.2.2.2 Nonhematologic Toxicity

Guidelines for dose modification in the event of nonhematologic toxicities are summarized in **Table 9**.

Table 9 Treatment Guidelines for Nonhematologic Toxicity

Symptom	Recommended Action	
	Lenalidomide	Carfilzomib
Blood and Lymphatic System		
Thrombotic microangiopathy (TMA) Fever, microangiopathic hemolytic anemia, thrombocytopenia, renal failure, neurologic changes		If the diagnosis is suspected, stop lenalidomide and carfilzomib and manage per standard of care including plasma exchange as clinically appropriate. If TMA is confirmed and related to lenalidomide or carfilzomib, permanently discontinue. If the diagnosis of TMA is excluded, lenalidomide and carfilzomib dosing may be resumed at full dose if clinically appropriate.
Cardiac		
Congestive heart failure	Full dose	Any subject with symptoms of congestive heart failure, whether or not drug related, must have the dose held until resolution or return to baseline, after which treatment may continue at a reduced dose, or the subject may be permanently discontinued. If no resolution after 4 weeks, the subject will be withdrawn from all study treatment.
Hypertensive crisis Sustained or persistent SBP \geq 180 mm Hg or DBP \geq 110 mm Hg	Full dose	Hold carfilzomib until resolution to baseline, then resume at 1 dose decrement
LVEF Reduction < 40% or < 55% if the drop is greater than 20% from baseline	Full dose	Hold carfilzomib until LVEF returns to \geq 40% or, if held due to a drop to < 55%, to within 15% of baseline. Resume at 1 dose decrement.
Infections and Infestations		
Infection Grade 3 or 4		Hold both lenalidomide and carfilzomib until systemic treatment for infection is complete. If ANC $>$ 1,000/ μ L, resume both drugs at full dose. If ANC $<$ 1,000/ μ L, follow hematologic toxicities dosage guidelines.
Hepatic Dysfunction and Related Investigations		
Mild liver dysfunction, defined as 2 consecutive values, at least 28 days apart, of: (1) total bilirubin ($>$ 33% direct) $>$ 1x ULN to $<$ 1.5x ULN OR (2) an elevation of AST and/or ALT with normal bilirubin	Full dose.	25% dose reduction. Dose may be re-escalated if liver function tests return to normal and drug-induced hepatotoxicity is excluded.

Page 1 of 3

Footnotes defined on last page of table

Table 9 Treatment Guidelines for Nonhematologic Toxicity (cont'd)

Symptom	Recommended Action	
	Lenalidomide	Carfilzomib
Hepatic Dysfunction and Related Investigations (cont'd)		

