Moderate liver dysfunction, defined as 2 consecutive values, at least 28 days apart, of total bilirubin (> 33% direct) > 1.5x ULN to < 3x ULN	Hold lenalidomide until resolution to baseline, then resume at full dose.	25% dose reduction. Dose may be re-escalated if liver function tests return to normal and drug-induced hepatotoxicity is excluded.
Grade 3 elevation in ALT and/or AST (> 5x ULN)	Hold lenalidomide until resolution to baseline, then resume at full dose.	Hold carfilzomib until resolution to baseline. Monitor any abnormality weekly. Resume carfilzomib with a 25% dose reduction if drug-induced hepatotoxicity is excluded.
Grade 3 elevation in total bilirubin	Hold lenalidomide until resolution to baseline, then resume at full dose.	Hold carfilzomib until resolution to baseline. Monitor total bilirubin and direct bilirubin weekly. Upon resolution of total bilirubin to normal, resume carfilzomib dosing with a 25% dose reduction if drug-induced hepatotoxicity is excluded.
Renal Dysfunction		
CrCl ^a ≥ 30 and < 50 mL/min	Reduce dose to 10 mg once daily.	Full dose
CrCl ^a ≥ 15 and < 30 mL/min (NCI-CTCAE Grade 3)	Hold dose. If CrCl recovers resume dose at 1 dose decrement. If significant CrCl reduction reappears then reduce dose to 15 mg every 48 hours. Further dose modification will be based on individual subject treatment tolerance.	Full dose
CrCl ^a < 15 mL/min (NCI-CTCAE Grade 4)	Hold dose. If CrCl recovers to baseline, resume dose at 1 dose decrement. If significant CrCl reduction reappears reduce dose to 15 mg every 48 hours. If dialysis required, reduce dose to 5 mg once daily (administer the lenalidomide after dialysis on dialysis days). Further dose modification will be based on individual subject treatment tolerance.	Hold dose. When CrCl returns to ≥ 15 mL/ minute, resume same dose. If dialysis required, contact the medical monitor.

Table 9 Treatment Guidelines for Nonhematologic Toxicity (cont'd)

Symptom	Recommended Action	
	Lenalidomide	Carfilzomib
Metabolism		
Tumor Lysis Syndrome 3 or more of the following: 
• increase in creatinine of \geq 50%• increase in uric acid of \geq 50%• increase in phosphate of \geq 50%• increase in potassium of \geq 30%• decrease in calcium, OR increase in LDH of \geq 2-fold from baseline	Hold both lenalidomide and carfilzomib until all abnormalities in serum chemistries have resolved; resume at full dose.	
Nervous System Disorders		

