Neuropathy Treatment-emergent painful grade 2, or grade 3	Full dose	Hold carfilzomib until resolution to \leq grade 2 without pain, then resume at 1 dose decrement
Neuropathy Grade 4	Discontinue	Discontinue
Posterior Reversible Encephalopathy Syndrome (PRES) headaches, altered mental status, seizures, visual loss and hypertension	If PRES is suspected, hold lenalidomide and carfilzomib. Consider neuroradiographic imaging, specifically MRI, to evaluate onset of visual or neurological symptoms suggestive of PRES. If the diagnosis of PRES is excluded lenalidomide and carfilzomib dosing may resume at the same dose, if clinically appropriate. If condition recurs, permanently discontinue carfilzomib.	
Respiratory		
Dyspnea Grade 2, 3 or 4	Full dose	Hold carfilzomib until resolution to baseline, then resume at 1 dose decrement
Pulmonary hypertension: (\geq Grade 3)	Full dose	Hold carfilzomib until resolution to baseline, then resume at 1 dose decrement
Pulmonary toxicity Interstitial lung disease, acute respiratory failure, ARDS (\geq Grade 3)	Hold lenalidomide until resolution to baseline then resume full dose	Hold carfilzomib until resolution to baseline, then resume at 1 dose decrement
Other Symptoms Not Listed Above		
Any other drug-related nonhematologic toxicity \geq Grade 3 ^b	For lenalidomide attribution, hold dose. Resume at 1 dose decrement when toxicity has resolved to Grade 1 or less or to baseline grade.	For carfilzomib attribution, hold dose. Resume at 1 dose decrement when toxicity has resolved to Grade 1 or less or to baseline ^c grade.

ALT = alanine aminotransferase; ANC = absolute neutrophil count; ARDS = acute respiratory distress syndrome; AST = aspartate aminotransferase; CrCl = creatinine clearance; DBP = diastolic blood pressure; KRD = carfilzomib/lenalidomide/dexamethasone; LDH = lactate dehydrogenase; LVEF = left ventricular ejection fraction; MRI = magnetic resonance imaging; NCI-CTCAE = National Cancer Institute-Common Terminology Criteria for Adverse Events; PRES = posterior reversible encephalopathy syndrome; SBP = systolic blood pressure; TMA = Thrombotic microangiopathy; ULN = upper limit of normal.

- ^a For a rapid fall from baseline in CrCl or an absolute fall of ≥ 60 mL/min, contact the medical monitor.

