10.1.6 CLINICAL LABORATORY TESTS

Clinical laboratory assessments will include the following:

- Hematology: hemoglobin, hematocrit, white blood cell (WBC) with complete differential (total neutrophils, lymphocytes, monocytes, eosinophils, basophils), RBCs, platelet count
- Full serum chemistry panel: sodium, potassium, chloride, bicarbonate, blood urea nitrogen (BUN), creatinine, glucose, calcium, magnesium, phosphate, AST, ALT, total protein, albumin, alkaline phosphatase, total bilirubin, uric acid, and lactate dehydrogenase (LDH)
- Abbreviated chemistry panel: sodium, potassium, chloride, bicarbonate, BUN, creatinine, glucose
- Coagulation tests: prothrombin time, activated partial thromboplastin time, and international normalized ratio

Hematology and serum chemistry (full or abbreviated) will be performed at Screening, on Days 1, 8, and 15 of each cycle, and at EOT. On Days 8 and 15 of each cycle, from Cycle 2 onwards, an abbreviated serum chemistry panel may be performed. Coagulation will be performed at baseline and at EOT. For screening laboratory samples, historical panel may be used if within 21 days prior to dosing on Cycle 1 Day 1. Thereafter, hematology samples

may be obtained anytime within the 24 hours prior to the carfilzomib administration, and full or abbreviated chemistry panels may be performed up to 72 hours prior to carfilzomib administration.

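### Table 9's liver rules: Day 1 tests drawn within the allowed windows can miss the 28-day spacing, and Grade 4 bilirubin is left out of the bilirubin row (minor)

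*Protocol*

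**What the plan says.** The rules are in Protocol 9.2.2.2, Table 9.

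- **Mild row:** "Mild liver dysfunction, defined as 2 consecutive values, at least 28 days apart, of" either bilirubin above 1x and below 1.5x ULN, or raised AST/ALT with normal bilirubin. Carfilzomib is cut by 25%; lenalidomide is unchanged.
- **Moderate row:** "Moderate liver dysfunction, defined as 2 consecutive values, at least 28 days apart, of total bilirubin" above 1.5x and below 3x ULN. Carfilzomib is cut by 25% and lenalidomide is held until baseline.
- **Bilirubin row:** "Grade 3 elevation in total bilirubin", with no numeric limit. Both drugs are held to baseline and bilirubin is checked weekly. For carfilzomib: "Upon resolution of total bilirubin to normal, resume carfilzomib dosing with a 25% dose reduction if drug-induced hepatotoxicity is excluded". Lenalidomide returns at full dose.
- **Catch-all row**, for other drug-related nonhematologic toxicity of Grade 3 or above: "For carfilzomib attribution, hold dose. Resume at 1 dose decrement when toxicity has resolved to Grade 1 or less" or to baseline. For lenalidomide: "For lenalidomide attribution, hold dose", with the same one-decrement restart.

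Section 10.1.6 and Appendix A set the testing. The full panel, which contains the liver tests, is drawn on Days 1, 8 and 15 of Cycle 1 and on Day 1 of each later cycle. On Days 8 and 15 from Cycle 2 a shorter panel is permitted: "Abbreviated chemistry panel: sodium, potassium, chloride, bicarbonate, BUN, creatinine, glucose". It has no AST, ALT or bilirubin. Section 9.1 lets each cycle start 28 ± 2 days after the last, and 10.1.6 lets chemistry be drawn up to 72 hours before carfilzomib.

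**The concern.** The spacing in the mild and moderate rows equals the planned interval between Day 1 tests, so it has no slack, while the visit windows allow shorter intervals. A subject with a persistent abnormality, seen at two fully compliant visits, can fail the criterion. The carfilzomib reduction, and in the moderate row the lenalidomide hold, then waits for another cycle.

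The word 'consecutive' adds a second problem. A site that chooses full panels on Days 8 and 15 puts extra values between the Day 1 values, so closer monitoring disables the rule.

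The bilirubin row leaves out the more severe grade. A Grade 4 rise that the investigator does not attribute to a study drug triggers no hold written in Table 9, whereas a Grade 3 rise holds both drugs whatever its cause. At stake is protection of individual subjects and uniform dosing across sites. No effect on an endpoint or analysis is claimed.

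**Working it through.** The plan states no figure to reproduce; the check is schedule arithmetic and a comparison of rows.

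**1. Day 1 pairs from Cycle 2.** Let L be the cycle length (26 to 30 days, section 9.1). Let a and b be the days by which the first and second draws precede their doses (0 to 3, section 10.1.6). The ±2 days on the Day 1 infusion is taken to be the same window as the cycle start.

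Gap = L + a − b. Minimum 26 + 0 − 3 = 23; maximum 30 + 3 − 0 = 33. On time, 28 + 0 − 0 = 28, which just qualifies.

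There are 5 × 4 × 4 = 80 combinations. The difference a − b takes the values −3 to 3 in 1, 2, 3, 4, 3, 2 and 1 ways. Combinations with a gap under 28:

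| L | Needs a − b | Count of 16 |
|---|---|---|
| 26 | ≤ 1 | 13 |
| 27 | ≤ 0 | 10 |
| 28 | ≤ −1 | 6 |
| 29 | ≤ −2 | 3 |
| 30 | −3 | 1 |

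Total 33 of 80 (41%). If only cycle length varies, 2 of 5 fail; if only draw day varies, 6 of 16 fail. None falls below 23.

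**2. Sites running full panels weekly.** Consecutive gaps are 7, 7 and 14 days. The longest in-window gap is Day 15 to the next Day 1: 14 + 2 + 2 + 3 = 21. No consecutive pair reaches 28.

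**3. Boundaries.** At exactly 1.5x ULN, the mild row needs less and the moderate row needs more, so neither applies. At exactly 3x ULN the moderate row does not apply.

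**4. Grade 3 against Grade 4 bilirubin.** The AST/ALT row has only a lower limit (5x ULN), so higher values stay in it. The bilirubin row has no such limit, and Table 9 names Grade 4 where it means to include it (infection, dyspnea, neuropathy).

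| | Grade 3 bilirubin row | Grade 4 via catch-all |
|---|---|---|
| Hold | both drugs, any cause | each drug only if attributed to it |
| Weekly bilirubin check | yes | not stated |
| Carfilzomib restarts when | bilirubin normal and drug-induced hepatotoxicity excluded | Grade 1 or less, or baseline |
| Carfilzomib from 56 mg/m² | 0.75 × 56 = 42 | 45 (Table 5) |
| Carfilzomib from 70 mg/m² | 0.75 × 70 = 52.5 | 56 (Table 5) |
| Lenalidomide from 25 mg | 25 | 15 (Table 6) |

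For carfilzomib, every line is looser at Grade 4. For lenalidomide, the hold is looser but the restart dose is stricter.

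**The case against.** **Persistence is the sponsor's choice.** A reader might infer that the rule wrongly delays action on abnormalities arising in Cycle 1, since no consecutive pair starting there can reach 28 days. The documents do not support calling that a drafting error. Arm 3 subjects enter with normal liver tests, so a new abnormality is first seen on Day 8 or 15. Adding 28 days gives Day 36 or 43, and on schedule the next required liver test is Cycle 3 Day 1 (Day 57). The wait follows from requiring 28 days' persistence, even without the word 'consecutive'. Shortening that period is a clinical trade-off, and Amendment 3 states an aim of giving full 20/56 dosing, although it says so of the eligibility change.

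**The 41% is not a failure rate.** This stands. It weights all allowed days equally, actual visit timing is not given, and sites control the early draw. Appendix A also plans the shorter panel on Days 8 and 15, so the weekly-panel case depends on a site using the latitude in 10.1.6.

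**Table 9 is guidance, with discretion.** Section 9.2.2 says carfilzomib and/or lenalidomide "may be held temporarily in the event of a treatment-related toxicity". This softens the effect, but it covers treatment-related events and does not supply a reduction that applies whatever the cause.

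**Grade 4 may not belong in the catch-all.** That row is headed for symptoms not listed above, and bilirubin is listed. On that reading Grade 4 has no row at all, which is no better. A reader might also infer that Grade 4 is treated more loosely throughout; the lenalidomide restart shows otherwise.

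**The boundary gap is trivial.** Largely so: only exact equality is affected, and at 1.5x both neighbouring rows cut carfilzomib by 25%. They differ on lenalidomide.

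**Conclusion.** The point holds as a minor wording fault in three rows. Compliant Day 1 pairs run 23 to 33 days, so a persistent abnormality can miss the criterion and wait at least one more cycle. The count is 0 if visits are on time and 33 of 80 if every allowed day is counted once. Where full panels are run weekly, the literal rule cannot be met.

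The Grade 4 omission matters mainly through attribution: an unattributed Grade 4 rise triggers no hold written in Table 9. The carfilzomib restart difference is small (45 against 42 mg/m² from 56). Appendix I explains that severe impairment, bilirubin above 3x ULN, means holding both drugs, with no attribution test. It is used here only as evidence of intent, and the finding does not rest on a mismatch with it.

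The conclusion assumes a literal reading of 'consecutive' and whole-day windows. How often these liver events occur is not given, so the number of subjects affected cannot be estimated.

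**What to change.** 1. In the mild and moderate rows, replace the spacing condition with: 'abnormal on Day 1 of 2 consecutive cycles (at least 23 days apart), with no normal value between', where abnormal means within that row's limits. This keeps one-cycle persistence, accepts every in-window Day 1 pair and works for sites running weekly full panels.
2. Change '< 1.5x' to '≤ 1.5x' and '< 3x' to '≤ 3x', the form used in Appendix I.
3. Relabel the bilirubin row 'Grade 3 or 4 elevation in total bilirubin', and keep the one-decrement lenalidomide restart for Grade 4.

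The cost is wording in three rows, with no added tests. The downside is a few more dose reductions, for abnormalities confirmed at 23 to 27 days rather than 28 or more. Onset on Cycle 1 Day 8 or 15 would still be acted on at about Day 57, which leaves the sponsor's choice of persistence unchanged.

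### Table 9's renal instructions for lenalidomide conflict with the Table 6 dose ladder at the 5 mg level, where two steps worded as reductions would raise the average daily dose

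*Protocol*

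**What the plan says.** Protocol Section 9.2.2, Table 6, gives the lenalidomide ladder. From a nominal 25 mg the reduced levels are 15, 10 and 5 mg, and the row ends there. From a nominal 10 mg the entries read "10 5 Discontinue". All opened groups start at 25 mg, since the 10 mg cohort (Cohort 3) was never opened (Protocol Figure 1, footnote a; SAP Table 1).

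The renal rows of Table 9 (Section 9.2.2.2) say, for lenalidomide:

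- Row 1, CrCl 30 to below 50 mL/min: "Reduce dose to 10 mg once daily".
- Row 2, CrCl 15 to below 30: "Hold dose. If CrCl recovers resume dose at 1 dose decrement", and then "If significant CrCl reduction reappears then reduce dose to 15 mg every 48 hours".
- Row 3, CrCl below 15: a hold, and one decrement once CrCl is back to baseline. On recurrence, "If significant CrCl reduction reappears reduce dose to 15 mg every 48 hours". Separately, "If dialysis required, reduce dose to 5 mg once daily".

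Rows 2 and 3 end by leaving later changes to the individual subject's tolerance. No row makes its fixed target depend on the dose being taken at the time.

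Section 9.2.2 also has a general rule on re-escalation. Once a reduced level has been tolerated for a full cycle, "the subject may, at the investigator's discretion, resume the dose level prior to the reduction". That sentence does not mention CrCl.

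**The concern.** Table 6 works by relative steps from the current dose, while the renal rows partly work by fixed targets. The two systems fit together only while the subject's dose is at or above the target. Both fixed targets that Table 9 words as reductions, 10 mg/day and an average of 7.5 mg/day, lie above the lowest Table 6 level of 5 mg/day. For a subject at that level, a site that follows the table to the letter would give more lenalidomide because renal function had worsened.

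This is first a matter of subject safety and of consistent conduct across about 30 sites. It also touches the primary endpoint, which is safety and extent of exposure (Protocol Section 13.1.1). The SAP lists acute renal failure and cytopenias as events of interest (Section 9.6.1), and it summarises lenalidomide relative dose intensity and dose changes (Section 9.6.7). Sites that read the same row differently would feed different dosing into those summaries.

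**Working it through.** **Inputs.** Ladder of 25, 15, 10 and 5 mg daily (Protocol Table 6). Fixed renal targets of 10 mg daily, 15 mg every 48 hours, and 5 mg daily on dialysis (Table 9). Dosing on Days 1–21 of each 28-day cycle (Section 9.2.1).

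**The plan's own conversion.** Table 2 gives maximum weekly lenalidomide exposure as 175 mg at 25 mg daily and 70 mg at 10 mg daily. Daily dose × 7 reproduces both: 25 × 7 = 175 and 10 × 7 = 70.

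**Average daily dose of the alternate-day target.** 15 mg / 2 days = 7.5 mg/day.

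**Change from the current dose** = target average / current dose − 1:

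| Current dose | To 10 mg daily | To 15 mg every 48 h (7.5 mg/day) | To 5 mg daily (dialysis) |
|---|---|---|---|
| 25 mg | −60% | −70% | −80% |
| 15 mg | −33% | −50% | −67% |
| 10 mg | 0% | −25% | −50% |
| 5 mg | **+100%** | **+50%** | 0% |

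The rise is confined to the 5 mg line. Counting actual doses in Days 1–21 does not remove it. Daily 5 mg gives 21 × 5 = 105 mg. Ten doses of 15 mg give 150 mg (150/105 = 1.43, +43%), and eleven give 165 mg (165/105 = 1.57, +57%).

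**How a subject reaches 5 mg.**

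1. *Within the renal rows.* A 25 mg subject falls to CrCl 30 to below 50 and goes to 10 mg. A further fall to 15 to below 30 brings a hold. On recovery, one decrement from 10 mg is 5 mg on either row of Table 6. A second significant fall then triggers the 15 mg every 48 hours instruction: 7.5/5 = 1.5, or +50%.
2. *Through thrombocytopenia.* Under Table 7 each fall below the platelet threshold costs one lenalidomide step, so three falls give 25 → 15 → 10 → 5. A later fall to CrCl 30 to below 50 meets row 1: 10/5 = 2, or +100%.

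**Where the decrement starts.** Path 1 counts from the 10 mg taken before the hold. Counted from the nominal 25 mg, one decrement is 15 mg, so the subject would resume at 15/10 = 1.5 times the dose taken before the hold. On that reading the recurrence step is a true reduction (7.5/15 = 0.5, −50%), and the anomaly moves to the resumption. The protocol does not say which reading applies.

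**Rows 1 and 2 against each other.** Row 2 asks only that CrCl recover, whereas row 3 asks for recovery to baseline. Take a 25 mg subject who falls directly to CrCl 15 to below 30 and recovers only to 30 to below 50. Row 2 gives 15 mg (one decrement from 25), and row 1 gives 10 mg for the CrCl now present. This conflict needs no earlier reduction.

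**The case against.** The strongest reply is that the table does not operate alone and that the conflict sits in a corner of it. Table 9 is headed as recommended action under guidelines, and an investigator may well take the word reduce as ruling out an increase. Rows 2 and 3 defer to individual tolerance. Every lenalidomide hold must be notified to the medical monitor within 2 business days (Section 9.2.2), and path 1 necessarily includes a hold. Footnote a of Table 9 sends a rapid CrCl fall, or an absolute fall of at least 60 mL/min, to the monitor. Section 8.2 requires the prescribing-information precautions and restrictions for lenalidomide to be observed. These points make a literal error less likely. None of them limits the fixed target to the current dose or settles the starting point of the decrement, so the contradiction stands.

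A reader might also infer more than the documents support:

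- *That any subject already lowered on the ladder would be given more.* The table above shows a rise only from 5 mg.
- *That ordinary stepwise renal decline leads there.* Path 1 needs a recovery and a second fall. Decline without recovery ends in a hold.
- *That the recurrence instruction raises the dose on either reading of the decrement.* Counted from 25 mg it halves the dose. The 10 to 15 mg rise on that reading comes at resumption, after CrCl has recovered.
- *That the re-escalation sentence sends a subject back to 25 mg with CrCl still below 50.* That sentence is permissive, and row 1 continues to apply to the current CrCl, with creatinine measured on Days 1, 8 and 15 of each cycle (Section 10.1.6). What remains is that the protocol does not state how the two interact.
- *That the safety summaries would be materially distorted.* The SAP plans no formal hypothesis testing (Section 2.2), and nothing in the documents shows how many subjects would be involved.

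**Conclusion.** The conflict holds in a limited form. For a subject at 5 mg/day, two Table 9 instructions worded as reductions exceed the current dose, by 100% (10 mg daily) and by 50% (15 mg every 48 hours). From every higher level they lower or keep it. Two gaps go with this: the decrement after a renal fixed dose has no stated starting point (5 mg or 15 mg results), and rows 1 and 2 give 10 mg and 15 mg for the same partial recovery from 25 mg. The unstated link to the re-escalation sentence is secondary.

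The 50% and 100% figures assume a literal reading of the rows. The renal route to 5 mg also assumes that the decrement is counted from the dose taken before the hold. The number of subjects affected cannot be derived. It is probably small, because each route needs several separate events, but that is a judgement rather than a calculation. The point is relevant to safety and should be corrected; it does not reach the highest severity.

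**What to change.** The sponsor should reconcile the renal rows of Table 9 with Table 6 and with the re-escalation sentence in Section 9.2.2. The revised text should settle four things:

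- how the fixed renal targets apply to a subject already at the 5 mg level;
- the dose from which a single decrement is counted after a renal fixed dose;
- which row governs when CrCl recovers only to 30 to below 50 mL/min;
- how the re-escalation sentence works while CrCl remains in a renal row.

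The choice of doses and clinical rules belongs to the sponsor, and none is proposed here. The cost is a wording change to one table and one sentence, by amendment or by a clarification letter to sites. It needs no new data, visits or analyses.

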19. Pleural effusions requiring thoracentesis within 14 days prior to Cycle 1 Day 1
20. Ascites requiring paracentesis within 14 days prior to Cycle 1 Day 1
21. Ongoing graft-versus-host disease
22. Uncontrolled hypertension or uncontrolled diabetes
23. Significant neuropathy (\geq Grade 3) within 14 days prior to Cycle 1 Day 1
24. Known cirrhosis
25. Known human immunodeficiency virus (HIV) infection, hepatitis C infection, or hepatitis B infection (subjects with hepatitis B surface antigen [SAg] or core antibody receiving and responding to antiviral therapy directed at hepatitis B are allowed)
26. Participation in another interventional study within 28 days prior to Cycle 1 Day 1
27. Major surgery (except kyphoplasty) within 28 days prior to Cycle 1 Day 1
28. Female subjects who are pregnant or lactating
29. Any other clinically significant medical disease or social condition that, in the investigator's opinion, may interfere with protocol adherence or a subject's ability to give informed consent

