- ^b In the event of a possible drug-related nonhematologic toxicity, the investigator should, to the best of his/her ability, assess its relationship to lenalidomide, carfilzomib, dexamethasone, or the combination of KRD to the extent possible. If both carfilzomib and lenalidomide are considered likely to be involved, then recommended actions for both should be instituted. For nonhematologic toxicity likely due to dexamethasone, refer to [Table 11](#) for treatment guidelines for dexamethasone-related toxicity.
- ^c For grade 3 hypertension, baseline refers to an average SBP < 140 mmHg or DBP < 90 mmHg on appropriate antihypertensive therapy.

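### Table 9 footnote c lets carfilzomib restart after grade 3 hypertension once either systolic or diastolic pressure is below its limit, even if the other is still raised

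*Protocol*

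**What the plan says.** Protocol Table 9 (Section 9.2.2.2) deals with systemic hypertension in two places.

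- **Hypertensive crisis row.** It applies to sustained or persistent systolic pressure of 180 mmHg or more, or diastolic pressure of 110 mmHg or more. The carfilzomib action is "Hold carfilzomib until resolution to baseline, then resume at 1 dose decrement". The row carries no footnote c marker.
- **Catch-all row.** It is headed "Any other drug-related nonhematologic toxicity" and covers Grade 3 and above. The carfilzomib cell reads "For carfilzomib attribution, hold dose. Resume at 1 dose decrement when toxicity has resolved to Grade 1 or less or to baseline". This is the only cell in the table with the footnote c marker.

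Footnote c then states: "For grade 3 hypertension, baseline refers to an average SBP < 140 mmHg or DBP < 90 mmHg on appropriate antihypertensive therapy".

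Three other provisions bear on the point:

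- Exclusion criterion 22 (Section 6.2) bars "Uncontrolled hypertension or uncontrolled diabetes" at entry and gives no numeric limit.
- Section 9.2.2 lets the investigator hold carfilzomib for treatment-related toxicity at discretion.
- Section 9.2.2 also provides that, if the reduced dose is tolerated for a full cycle, the subject may, at the investigator's discretion, "resume the dose level prior to the reduction at the start of the subsequent cycle".

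**The concern.** Footnote c acts as a release condition: it decides when a held subject may be dosed again. A trigger for holding a drug properly joins its limits with *or*, as the crisis row does, because either raised component is reason enough to stop. A release condition built on control needs *and*, because pressure is controlled only when neither component is raised. Footnote c uses the trigger's connective for the release.

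A subject held for raised systolic pressure can therefore be released on a diastolic value that may never have been abnormal. For such a subject the numeric limits do not test recovery at all. The stake is re-exposure to carfilzomib while the component that caused the hold is still uncontrolled, in a trial whose primary objective is safety and tolerability and whose SAP (Section 9.6.1) lists hypertension as an event of interest.

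**Working it through.** No statistical figure is involved. The check is a comparison of two logical conditions.

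**Inputs**

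- Release condition as written (footnote c): SBP < 140 *or* DBP < 90, averaged, on treatment.
- Alternative: SBP < 140 *and* DBP < 90, averaged, on treatment.
- Upper bound (crisis row): readings with SBP ≥ 180 or DBP ≥ 110 fall under a separate rule and are set aside.
- Dose steps (Table 5): 70 to 56 mg/m² and 56 to 45 mg/m².

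**Where the two conditions differ.** The *or* condition is true and the *and* condition false exactly when one component is below its limit and the other is not. Removing crisis readings leaves two regions:

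- SBP 140 to 179 with DBP < 90
- DBP 90 to 109 with SBP < 140

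**Worked readings**

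| Average on therapy | SBP < 140 | DBP < 90 | Meets *or* (as written) | Meets *and* | At crisis limit |
|---|---|---|---|---|---|
| 165/85 | no | yes | yes | no | no |
| 135/105 | yes | no | yes | no | no |
| 150/95 | no | no | no | no | no |
| 141/91 | no | no | no | no | no |
| 135/85 | yes | yes | yes | yes | no |
| 185/85 | no | yes | set aside | set aside | yes |

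The written definition accepts 165/85 and rejects 141/91, although the second systolic value is 165 − 141 = 24 mmHg lower. It therefore does not track how well pressure is controlled.

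**Does other text close the gap?**

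- Resolution to Grade 1 or less is a second route to restart, joined to the baseline route by *or*. It adds no requirement to the baseline route.
- The crisis row covers only higher pressures and does not use footnote c.
- Section 9.2.2.3 lists conditions for which drug need not be held. Hypertension is not among them.
- No current passage says both limits must be met.

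**Dose at restart.** One decrement is 1 − 56/70 = 20.0%, or 1 − 45/56 = 19.6%. These are the ordinary Table 5 steps, not an effect of the footnote. They show the level at which a subject released in the gap would be re-exposed.

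**The case against.** The strongest reply is that the footnote should not be read apart from its rule. The cell asks for the toxicity to have resolved, and 165/85 is hard to call resolved in a subject held for systolic pressure. A sensible investigator would apply each limit to whichever component was raised. This may have been the intent, but the text does not say so, and a site that restarted at 165/85 would be following the written definition.

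Second, Table 9 gives recommended actions, and several safeguards surround it:

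- The reading must be an average on suitable antihypertensive treatment.
- Restart is one step down.
- The investigator may hold for longer.
- The medical monitor must be told of a hold within 2 business days (Section 9.2.2).
- Cycle delays of more than 2 days must be discussed with the monitor (Section 9.1).
- Resting pressure is taken before carfilzomib on Days 1, 8 and 15 of every cycle (Section 10.1.2).

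These stand as mitigation and keep the point minor. They permit caution but do not require it.

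Third, some limits on the evidence stand:

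- The documents give no CTCAE blood pressure cut-offs, so they do not show whether 141/91 could restart by the Grade 1 route, or what grade the upper part of the gap would carry.
- Exclusion 22 has no number, so it cannot be compared directly with the footnote.
- Appendix I says only Arm 3 (20/56 mg/m²) enrolls under Amendment 3, so the 70 to 56 step concerns subjects already enrolled.
- With *and*, a subject whose stable pressure at entry was, say, 145/80 would have to improve on it unless the Grade 1 route applied, which could prolong an interruption of myeloma treatment.

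None of these changes what the footnote's two limits accept.

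**Conclusion.** The concern holds. As written, footnote c treats a subject as back to baseline when only one pressure component is below its limit. Below the crisis limits, that admits SBP 140 to 179 with DBP < 90, and DBP 90 to 109 with SBP < 140.

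The conclusion rests on the literal wording and on the absence of any other text requiring both limits. It starts from a subject already held for grade 3 hypertension, so it needs no CTCAE cut-offs. The number of subjects affected cannot be estimated from the documents.

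This is a minor safety-rule error that should be corrected. The footnote does not enter the DLT definition, any analysis set or any endpoint.

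**What to change.** In Table 9 footnote c, replace *or* with *and* between the two limits, so that the average systolic pressure must be below 140 mmHg and the average diastolic pressure below 90 mmHg, both on treatment, before the baseline route to restart is met. With that change, 165/85 and 135/105 no longer qualify by that route, and 135/85 still does.

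The cost is one word. The readings are already collected under Section 10.1.2, and sample size and analyses do not change. Some subjects may be held longer. By how much cannot be judged from the documents.
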